The combination of elaborate marketing campaigns in social media and the research app will allow for a very efficient recruitment, eligibility check and data collection. Those being interested will register online after confirming inclusion criteria: 1) between the ages of 16-19, 2) have previously sought professional help for anxiety and/or depressive symptoms, 3) have been feeling fine or mostly fine for the last two months. Before further assessment and trial inclusion, the adolescent will sign informed consent digitally. After consent is obtained, they will be invited to download the research app. To ensure eligibility, preassessment with the digitalized self-report format of the clinical interview Composite International Diagnostic Interview 5th revision (CIDI 5.0 (31)) will be conducted to make sure that the adolescent have had a previous episode of depression and/or an anxiety fulfilling the DSM-5 criteria, and no current ongoing episode or ongoing anxiety disorder before trial entry and randomization are conducted.

Table 1. Participant eligibility

Inclusion criteria

 • Currently in full or partial remission for a minimum of 2 months from a depressive disorder or an anxiety disorder. • Age between 16-19. • Native or fluent Norwegian or Scandinavian language skills. • Willingness to take part even when allocated to the non-preferred intervention.
Exclusion criteria

 • Ongoing depressive disorder, ongoing anxiety disorder. • Recent (within ~1 year) completion of the “Tankevirus”-intervention. • No available smartphone.

PRIMARY ENDPOINT: The primary endpoint will be time until relapse and number of relapses to depression during the 12-months follow-up post-randomization. To assess relapse, the app will give notifications for biweekly assessments with the ultra-brief PHQ-4 (32) assessing both anxiety and depressive symptoms. If the depression subscale indicates relapse (score ≥ 3), the remaining questions from PHQ-A (33), that is the adolescent version of PHQ-9 (34), will pop-up. The items in PHQ-9 aligns with the diagnostic criteria for major depressive disorder as described in the Diagnostic and

Statistical Manual of Mental Disorders (35) and an algorithm can therefore indicate depressive relapse (36). This procedure of biweekly assessments will also provide a precise measure of time to relapse.

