For exploratory purposes, we will also examine predictors of relapse and predictors for the efficacy of these respective interventions for investigating whom that are most likely to benefit from these different options. In line with recent developments in clinical research, we will address outcome domains relevant from the adolescent perspective, like well-being and self-reported symptom load (37), described below.

SECONDARY OUTCOMES (between trial entry, at 3 months, 6 months, and 12-months):

Repetitive negative thinking - RNT-10 (38) assess transdiagnostic repetitive negative thinking, such as worry and rumination. The questionnaire will be translated into Norwegian by means of a back-translation procedure.

Somatic complaints – SSS8 is an 8-item questionnaire about somatic complaints, freely available and translated into Norwegian (39).

Well-Being - EPOCH Measure of Adolescent Well-Being(40) is a 20-item validated questionnaire that is freely available and will be translated into Norwegian by means of a back-translation procedure.

Health related Quality of Life - EQ-5D-5L + EQ VAS (41, 42) is available in Norwegian and will be used for economic evaluation of the interventions.

Use of health care services – adapted version of the Client Service receipt inventory (CSRI) will assess use of health services, medication use, and school absence.

ASSESSMENTS: Assessments at baseline will serve as predictors of outcome, and include age, gender, parental educational level as proxy for socioeconomical status, in addition to the assessments listed as secondary outcomes. Adolescents are required to fill in questionnaires repeatedly at 3, 6 and 12-month follow up. To maintain fidelity to the trial and prevent fatigue, we have prioritized short, validated scales. All assessments will be conducted within a digital environment (i.e., the research app). In addition to the primary and secondary outcome, at 3-month follow-up, the 8-item Client Satisfaction Questionnaire adapted to Internet-based interventions (CSQ-I (43)) will be administrated to those taking part in one of the two interventional arms.

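### The relapse scale (PHQ-4/PHQ-A) is not listed at baseline, so entrants who pass the CIDI but already meet the PHQ-A algorithm cannot be told apart from early relapses, and no baseline depression score is available for adjustment

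*Protocol*

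**What the plan says.** All the relevant text is in protocol section 1.3.

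- **Eligibility (Table 1 and PARTICIPANTS).** Those admitted are "Currently in full or partial remission for a minimum of 2 months from a depressive disorder or an anxiety disorder". The online self-screen asks whether they "have been feeling fine or mostly fine for the last two months". A self-report CIDI 5.0 must then confirm a past episode and "no current ongoing episode or ongoing anxiety disorder before trial entry and randomization are conducted". Under ETHICS, anyone found to have an ongoing disorder is not included.
- **Endpoint (PRIMARY ENDPOINT).** Time to relapse and number of relapses are counted over 12 months from randomisation. For this, "the app will give notifications for biweekly assessments with the ultra-brief PHQ-4 (32) assessing both anxiety and depressive symptoms". A depression subscale score of 3 or more opens the remaining PHQ-A items, and an algorithm on those items indicates relapse.
- **Baseline (ASSESSMENTS).** "Assessments at baseline will serve as predictors of outcome, and include age, gender, parental educational level as proxy for socioeconomical status". The secondary measures are also taken at this point, namely RNT-10, SSS8, EPOCH, EQ-5D-5L with EQ VAS, and the CSRI.

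PHQ-4 and PHQ-A appear only as biweekly follow-up measures. No rule requires a participant to be PHQ-negative at the start before a relapse can count.

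**The concern.** Entry and endpoint are judged on different instruments, and the endpoint instrument has no starting value. Two things follow.

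First, in a sample that includes partial remission, some participants may pass the CIDI and still meet the PHQ-A algorithm on the day they are randomised. They would be recorded as relapsing at the first biweekly assessment. The app releases its modules over three weeks, and the group course has a wait of about one week before three weekly sessions. If the first assessment falls two weeks after randomisation, neither intervention is complete by then. Such events carry no treatment effect and pull the hazard ratio towards 1. They also enter the count of relapses.

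Second, no listed baseline measure is a depression-severity scale. Section 1.1 cites evidence that worry predicts relapse better than residual depression does, and it plans a mediation analysis of repetitive negative thinking on relapse. Without a baseline depression score, neither that analysis nor the predictor analyses can separate RNT from residual depressive symptoms. An SAP written later cannot supply a measurement that was never taken.

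**Working it through.** **Step 1: is the scale at baseline?** Set side by side, the baseline list (demographics plus five secondary measures) and the endpoint definition (PHQ-4, then PHQ-A) have no instrument in common. The CIDI is described as answering two yes/no questions: a past episode, and a current one.

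**Step 2: the plan's own figure.** STATISTICAL POWER gives 165 per group for HR 0.6, 15% annual dropout, one year, 0.05 level and 80% power. Two-sided testing is assumed.

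- Schoenfeld: 4 × (1.960 + 0.842)² / (ln 0.6)² = 31.4 / 0.261, so 121 events.
- Freedman: (1.6 / 0.4)² × (1.960 + 0.842)² = 16 × 7.85, so 126 events.
- Share of 2 × 165 = 330 participants: 121/330 = 36.7%; 126/330 = 38.2%.
- With control hazard λ and dropout hazard μ = −ln 0.85 = 0.1625, expected events are 165 × [g(λ) + g(0.6λ)], where g(x) = x/(x + μ) × (1 − exp(−(x + μ))). Solving for 121 and 126 events gives 12-month control relapse risks of 47% and 49%.

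The protocol does not state a control relapse risk. So 165 per group is plausible, but it cannot be strictly reproduced.

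**Step 3: effect of entry-positive participants.** A share p of each arm is assumed to be flagged at the first two-weekly visit; everyone else follows HR 0.6. Two-arm log-rank simulation, 165 per arm, 2,000 runs, control risk 47%, 15% annual dropout. Simulation error is about one percentage point.

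| p (assumed) | Counted as relapses: HR | Power | Removed, not replaced: HR | Power |
|---|---|---|---|---|
| 0% | 0.60 | 79% | 0.60 | 81% |
| 3% | 0.62 | 77% | 0.59 | 79% |
| 5% | 0.63 | 74% | 0.60 | 77% |
| 10% | 0.67 | 66% | 0.60 | 74% |

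The two 0% entries are the same scenario with different random draws, so both read as about 80%.

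Simulations at a control hazard of 0.665 per year (risk 1 − exp(−0.665) = 49%) gave HR 0.62, 0.63–0.64 and 0.66. Power was 76–77%, 74% and 68% when entry positives were counted, and 79%, 79% and 77% when they were removed.

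**Step 4: cross-check of the removal column.** Removing a share p leaves about 121 × (1 − p) events. Power is Φ(0.511 × √(events/4) − 1.96).

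- p = 0: 121 events, 80%.
- p = 3%: 117 events, 79%.
- p = 5%: 115 events, 78%.
- p = 10%: 109 events, 76%.

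This agrees with the simulations within their error. Removal restores the hazard ratio but only part of the power: about 2–3, 3–5 and 8–9 points at 3%, 5% and 10%.

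**The case against.** The strongest reply is that the CIDI already does most of this work. A reader might infer that any symptoms carried over from partial remission will be scored as relapse. The documents do not support that. A subscale score of 3 or more only opens further items, and relapse then requires an algorithm on items aligned with the criteria for major depressive disorder. To be miscounted, a participant must report feeling fine or mostly fine for two months, pass a screen for a current episode, and still meet that algorithm. The exposed group is therefore limited to CIDI/PHQ-A disagreement and near-threshold cases. This stands, and it limits the point.

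It is also fair that the baseline list is introduced as what the assessments include, and that the date of the first PHQ-4 is not given, so an entry assessment is not ruled out. Nothing provides for one, however, and a PHQ-4 alone would not be the full scale.

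CIDI answers and baseline RNT-10 could serve as partial covariates, so it would be too strong to say that entry symptoms cannot be adjusted for at all. What is missing is adjustment on the endpoint scale. Finally, the choice of covariates and the event-counting rule may sit in an SAP that is not shown. That is true of the analysis, but not of what is collected.

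**Conclusion.** The point holds in limited form. As written, the trial has no baseline value on the scale that defines its primary endpoint. CIDI-negative, PHQ-A-positive entrants cannot be separated from early relapses, and baseline depression severity is not available to the primary models or to the predictor and mediation analyses.

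A reader might go further and infer a biased comparison. That does not follow. With 1:1:1 randomisation such events are balanced in expectation, so the effect is dilution and lost precision. Nor would a baseline PHQ-A remove every event that occurs before the programmes are complete, because the clock starts at randomisation in any case.

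The size is unknown. Under the assumed 3% to 10% shares and the assumed control risk of 47% to 49%, the observed HR would be about 0.62 to 0.67 and power about 77% to 66%, against about 80% planned. The documents give neither input, and the shares make no estimate of how many such participants the CIDI would remove. The effects on the number-of-relapses analysis and on the precision gained by adjustment were not quantified.

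**What to change.** 1. Add the full PHQ-A to the preassessment in the research app, before randomisation, and list it under ASSESSMENTS.
2. Adjust the primary models for the baseline score, and carry it into the predictor and RNT mediation analyses.
3. Keep all randomised participants in the primary intention-to-treat analysis. Prespecify a sensitivity analysis that excludes those already PHQ-A-positive at baseline. Because the exclusion uses a pre-randomisation measurement, it preserves the randomised comparison.

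A rule that counts a relapse only after a sub-threshold assessment is less suitable for the primary analysis. It leaves undefined how the time at risk of entry-positive participants is handled under intention-to-treat.

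The cost is nine further items, once, in an app that is already to deliver the scale. The sensitivity analysis will have somewhat less power than planned, since excluded participants are not replaced. The change has to be made before enrolment, because the score cannot be recovered afterwards.

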1.2. Novelty and ambition

A main objective of this this multiarmed trial is to compare two digital versions of a transdiagnostic prevention program with varying level of therapist guidance, to assessment-only. The “Tankevirus”- (eng.: Thought viruses) program offers easily accessible, popularized knowledge and advice on how to develop psychological resilience. It is based on the principles of CBT and makes available different strategies for targeting heuristics and thinking traps leading to rumination and worry. By reducing thought viruses, risk of relapse can be reduced.

Digital interventions targeting mental health problems has grown profoundly more popular due to its availability, accessibility, scalability, and low cost associated with its use. Importantly, clinical trials investigating their effectiveness suggests that they offer value for money when compared with no intervention and non-therapeutic controls, but maybe not when controlled to interventions led by therapists (27). However, a direct comparison between digital interventions and therapist-led interventions in relation to relapse has not been conducted and no digital interventions for relapse prevention has been investigated in adolescent populations.

By investigating the efficacy of two types of digital interventions with different need for therapist involvement, and predictors for their effect, this trial will offer new insights and strategies for reducing relapse among adolescents, potentially paving the way for relapse prevention in the format of a readily accessible, personalized, digital solution for adolescents that can be easily implemented nationwide. By assessing the cost-effectiveness of the different versions of the interventions we can identify whether therapist involvement is necessary. While previous relapse prevention trials have shown efficacy (18), they have not been health economically evaluated. Digital intervention has an obvious economical advantage compared to individualized, therapist-guided interventions, however, the evidence regarding the cost-effectiveness of digital tools is scattered (28).

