1.3. Research questions and hypotheses, theoretical approach and methodology

RESEARCH QUESTION: Through a decentralized RCT investigating two digital interventions with differentiated levels of therapist-support, the goal is to expand knowledge about transdiagnostic relapse prevention strategies that can easily be scaled up and have the potential of cost-effectively reducing relapse rates for adolescents in an important phase of life. Alongside, collecting empirical

[figure not shown]
evidence for the association between repetitive negative thinking and relapse will increase knowledge regarding underlying mechanisms of relapse prevention strategies.

DESIGN: The trial is designed as a three-armed randomized single-blind open-label clinical trial (1:1:1) with stratification based on gender. It will not be possible to blind participants in the study due to the obvious differences between the interventions. We will investigate the effects of the “Tankevirus”-therapist-guided intervention and the “Tankevirus” smartphone app, respectively, and compare the effect of these transdiagnostic interventions to assessment only. All arms will be conducted in combination with care as usual. Assessments are done digitally, with no influence from the researcher. The primary endpoint of the trial will be analyzed blinded to treatment allocation. The trial will be preregistered with clinicaltrials.gov.

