- **Assessment-only:** All assessments will be conducted, but no intervention will be provided to this group. The assessment only condition is necessary for investigating natural trajectory and form the baseline level for assessing risk reduction in the interventional groups.

Figure 1. Screenshot from GooglePlay of the “Tankevirus” smartphone app.

All interventions and assessments for all trial arms will be fully digitalized through a research app, which is essentially a modification to the already developed “Tankevirus”-app, including all preassessments and follow-ups. Human interaction is limited to the therapist-led group, otherwise automated nudges and notifications will remind the adolescents to complete assessments. This will be beneficial when considering the scalability and implementation of the intervention, should it be successful, and for evaluating whether human interaction indeed is a driver of the effect between interventions.

HYPOTHESIS: The main hypothesis is that the outcome related to the therapist-guided group intervention will be more effective in reducing number of relapses and time to relapse during the follow-up period when compared to the app-based approach, and that the app-based approach will be more efficacious compared to an assessment-only condition/care-as-usual (the control group).

PARTICIPANTS: Participants will primarily be recruited through large scale marketing campaign in social media (i.e., TikTok, Snapchat, Instagram) and web pages of user organizations, informing about this trial and the opportunity to take part. This is the most efficient way of reaching eligible participants, as clinicians seldom refer to such a trial ([name], PI of the StayFine-trial targeting adolescents in remission, *personal communication*, 21.07.24). Overall, 90 % of Norwegian adolescents are on social media (30). Currently, we have established contact with the social media coordinator in Mental Helse Ungdom. We will also post physical adds at places we expect adolescents to see them. Through other ongoing projects we have contact with ~150 general practitioners and we have established a collaboration with the low-threshold service UngArena.

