STATISTICAL POWER: For the primary endpoint investigating number of relapses within the follow-up period, we will conduct a fixed effects omnibus ANOVA. Presuming Cohen's $f = .25$, alpha = .0167 (.05/3; Bonferroni corrected) and power = .8 including three groups, we will require a total sample size of 207 (GPower 3.1). Presuming 15 % dropout, we will need 238 adolescents to take part in the study. For time to relapse, the power analysis was performed using Monte Carlo simulation. A large pool of simulated survival data was generated, reflecting a hazard ratio of 0.6 between two groups, a 15% annual dropout rate with competing risk, and a 1-year observation period. The simulation titrated the sample size, drawing 10.000 random samples at each step and fitting Cox proportional hazards models. Power was estimated as the proportion of samples yielding statistically significant results at the 0.05 level. The analysis concluded that approximately 165 individuals per group, meaning that a total of 495 adolescents would be required to achieve 80% power for detecting a hazard ratio of 0.6 under the specified conditions. This simulation method accounts for the complexities of survival data, including censoring and limited observation time, providing a robust sample size estimate for the study design. All randomized participants will be subjected to analysis in accordance with an intention to-treat approach. The multiarmed parallel group randomized trial will be reported according to the extensions recommended by CONSORT (44).

RISK: Recruitment is the main risk factors of this trial. A few trials are currently under way in adolescent populations (e.g., StayFine trial (16), RuMeChange (15)) and in the first, they were in contact with 3018 adolescent during a three-year period. Their strict inclusion criteria and elaborate pre-inclusion assessments hindered several from participating, but still they had 589 eligible

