participants. Our pre-inclusion assessments and inclusion criteria will be less comprehensive, allowing for more participants to be included. Presuming that the three birth cohorts in Norway comprises 150.000 adolescents aged 16-19. Of these, 5 % will currently have an anxiety disorder and 2% will have a depressive disorder as per diagnosis in specialized health care (45), amounting to approximately 10.500 potential participants. We would then need to recruit 4.7 % of this population (495/10.500) to complete this study. When considering that we require the adolescents who are in remission only, that they may have fulfilled the criteria at earlier ages, and that only a minority of adolescents are diagnosed and/or treated in specialized health care even when having profound symptom load (46), these numbers are conservative.

Attrition is another risk factor. The evidence in relation to decentralized trials and retention among adolescents is still scarce, and recommendations currently rely on the use of well-evidenced strategies (e.g., incentives, reducing barriers and burden, and investing in building positive relationships with participants) when engaging adolescents in longitudinal health studies (47). Hence, the adolescents will be issued a universal gift card worth 1200 NOK when they have completed their participation. Each assessment will be initiated by a prompt about how much it's pays to promote its completion. The therapists in the therapist-led interventional arm have extensive experience delivering these interventions to youths and are good at building positive relations. Due to the digitalized format, push notification will be used to promote engagement.

ETHICS: There is an inherent risk of relapse among these adolescents, and it will therefore be important to detect if their state deteriorates during the trial and offer them advice on how they can proceed to receive the adequate level of care. The contact information to the project group will always be available in the app. At all follow-ups, if a certain symptom load is detected, a pop-up message will appear, including our contact information and information about treatment providers. If CIDI 5.0 pre-assessment reveals an ongoing disorder, the adolescent will be advised on whom to contact for receiving adequate level of care and will not be included in this trial.

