2.1. Potential impact of the proposed research

Should this trial be successful, we will have a scalable solution for breaking the unfortunate cycle of reoccurrence of depression among adolescents, which will have long-term beneficial impact. Based on prediction analysis, the two different alternatives of relapse prevention in this trial, including either clinician supported intervention or self-help intervention, allow for staging of care according to individual needs and cost-benefit calculations.

Anxiety and depression often go hand in hand with physical complaints. The “Tankevirus”-program targets transdiagnostic factors underlying physical complaints and pain and might therefore be beneficial in a broader health related context and reduce the overall burden associated with recurrent depression in adolescence on the health care system.

This trial will in addition to depression relapse, also investigate the diagnostic instability represented by the cross over from anxiety to depression. In this undescribed field of research, this represents a major leap when quantifying the potential benefit of introducing programs in an intermittent phase of the disorders and hinder its transgression into episodes of depression. Hence, this high-quality large-scale trial with long-term follow-up will provide evidence for the efficacy of depression relapse interventions among adolescents. The head-to-head comparison of interventions will disentangle the level of clinician-involvement required, and the inclusion of a cost-effectiveness analysis will bring leverage for its implementation.

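### The 80% power for number of relapses belongs to an omnibus ANOVA, not to the pairwise comparisons the trial sets out to make, and that ANOVA takes no account of follow-up time

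*Protocol*

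**What the plan says.** The primary endpoint has two parts, time to depressive relapse and number of relapses over 12 months. For the second part, section 1.3 (STATISTICAL POWER) states: "For the primary endpoint investigating number of relapses within the follow-up period, we will conduct a fixed effects omnibus ANOVA". The inputs are Cohen's f = 0.25, alpha .0167 (.05/3), three groups and 80% power, giving 207. It continues: "Presuming 15 % dropout, we will need 238 adolescents to take part in the study". The same paragraph adds: "All randomized participants will be subjected to analysis in accordance with an intention to-treat approach". No other test of the count is named or powered.

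The questions are put pairwise in four places:

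- Section 1.3, HYPOTHESIS: guided delivery is expected to do better, on number of relapses as well as time, "when compared to the app-based approach, and that the app-based approach will be more efficacious compared to an assessment-only condition/care-as-usual".
- Section 1.2: a main objective is to "compare two digital versions of a transdiagnostic prevention program with varying level of therapist guidance, to assessment-only".
- Section 1.3, DESIGN: the trial will "compare the effect of these transdiagnostic interventions to assessment only".
- Section 2.1: "The head-to-head comparison of interventions will disentangle the level of clinician-involvement required".

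The recruitment target comes from the time-to-relapse calculation, 165 per arm. Section 1.3, RISK, confirms it: "We would then need to recruit 4.7 % of this population (495/10.500) to complete this study".

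**The concern.** An omnibus F-test rejects when the three means are not all equal. It does not say whether guidance adds anything to the app, or whether the app beats assessment-only. Those are the two steps of the main hypothesis, and the first decides whether a therapist is needed.

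The alpha of .05/3 is what three pairwise tests would use, yet it is applied to a single omnibus test. The resulting 207 fits neither plan. If guided against assessment-only drives a significant F, the trial could report success on the count while both hypothesised steps stay unanswered. A reader would also take the 80% as power for the stated hypothesis, which it is not.

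Secondarily, the outcome is a count of events over time, 15% are expected to drop out, and everyone randomised is to be analysed. An ANOVA on raw counts treats someone who leaves at two months as if observed for twelve. The covariates named elsewhere in section 1.3 (days waiting for the group course, ongoing care) do not measure time observed.

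**Working it through.** **1. The plan's own figure.** One-way ANOVA, noncentral F with 2 and N − 3 degrees of freedom and noncentrality N·f², f = 0.25, alpha = .05/3:

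- N = 207: power 0.805. The smallest adequate N is 206, rounded up to 207 for three equal arms, so the stated figure reproduces.
- One omnibus test at alpha 0.05 would need 159.
- At 420 (495 × 0.85 = 420.75, or 140 per arm) omnibus power is 0.991; at 495 it is 0.997.

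**2. What f = 0.25 implies for pairs.** The protocol gives no means, so the pattern is my assumption. For ordered means with neighbouring gaps a and b in SD units, f² = (2/9)(a² + ab + b²). With f fixed, the smaller gap is largest when a = b. Even spacing is therefore the best case for the weaker step:

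- neighbouring d = 0.25/√(2/3) = 0.306
- outer d (guided vs assessment-only) = 2 × 0.306 = 0.612

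**3. Pairwise power, even spacing.** Two-sided noncentral t, pooled error df = 3n − 3, noncentrality d·√(n/2). For example, n = 140 gives 0.306 × √70 = 2.56. The last column is from simulation.

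| n per arm | alpha | each neighbouring contrast | guided vs assessment-only | both neighbouring |
|---|---|---|---|---|
| 69 (N = 207) | .0167 | 27% | 88% | about 3% |
| 69 | .05 | 43% | 95% | about 11% |
| 140 (495 less 15%) | .0167 | 56% | >99% | about 24% |
| 140 | .05 | 72% | >99% | about 47% |
| 165 (495, no loss) | .0167 | 65% | >99% | about 35% |
| 165 | .05 | 79% | >99% | about 60% |

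Testing at 0.05 only after a significant omnibus test barely changes a neighbouring contrast (0.723 at n = 140, 0.792 at n = 165).

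For scale, 80% per neighbouring contrast needs 225 per arm at .05/3 (675 evaluable; 675/0.85 rounds up to 795) or 169 per arm at 0.05 (507 evaluable; 507/0.85 rounds up to 597).

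**4. Other patterns, f still 0.25.**

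- App a quarter of the way between the outer arms: d = 0.147 and 0.441. Over 140 to 165 per arm, the weaker contrast has 12–14% at .0167 and 23–27% at .05. The stronger has 90–98% across both levels.
- Only one arm different: d = 0.25 × 3/√2 = 0.530. At .0167 each non-null pair has 76% at 69 per arm, 98% at 140 and 99% at 165. The remaining pair is then truly null.

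**5. Follow-up time.** Simulated counts with no treatment effect, 165 per arm, 20,000 replicates. Assumed: 0.4 or 0.63 relapses per year, overdispersion 1, exponential dropout. Type I error against nominal .0167, as rate 0.4 / rate 0.63:

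| Dropout by arm | ANOVA on counts | Rate test with follow-up time |
|---|---|---|
| 15/15/15% | 0.016 / 0.017 | 0.018 / 0.019 |
| 10/15/20% | 0.018 / 0.017 | 0.018 / 0.017 |
| 5/15/25% | 0.027 / 0.029 | 0.018 / 0.018 |

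**6. Dropout inflation.** 207 × 1.15 = 238.05, the stated 238. Having 207 left after 15% loss needs 207/0.85 = 243.5, so 244.

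**The case against.** The strongest reply is that no stated figure is false. The test is labelled omnibus, 207 is right for it, and 207 does not set the trial size. The binding 495 rests on a two-group hazard ratio of 0.6 tested at 0.05, which is a pairwise calculation. Contrasts after an omnibus test are ordinary content for an analysis plan that is not at hand, and .05/3 suggests that they are intended. Pairwise tests at 0.05 after the omnibus test would have 72–79% per neighbouring contrast under even spacing, not far below 80%. The 72% is also pessimistic, because biweekly assessment means that dropouts contribute data until they leave.

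Much of this stands. The size of the shortfall depends on the pattern of means. The protocol sets no rule that both steps must succeed together, so the joint figures describe the whole ordering and are not a success criterion. The follow-up-time effect is negligible unless dropout differs clearly between arms, and the protocol gives no reason to expect 5/15/25%.

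None of it turns the omnibus 80% into power for the stated hypothesis. The 495 was sized for the other half of the endpoint and does not bring the weaker step to 80% under any ordered pattern at f = 0.25. The one-arm-different pattern gives good power for its non-null pairs, but it contradicts a hypothesis in which both steps are non-zero. A later analysis plan can add contrasts, but it cannot make the protocol's power statement describe them.

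**Conclusion.** The concern holds. For the relapse count, the protocol names and powers a test that does not answer its own pairwise questions. At the 495 target and f = 0.25, the omnibus test has over 99% power. Under even spacing, each hypothesised step has 56–65% at .05/3 or 72–79% at 0.05. The lower ends assume that 15% contribute nothing; the upper ends assume that all 165 per arm contribute fully. Guided against assessment-only is well powered throughout. Uneven spacing lowers the weaker step, to 12–27% in the example above. These figures rest on f = 0.25, the assumed spacings and approximately normal group means.

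The missing follow-up-time term is a lesser fault. In simulation it raises type I error only when dropout is clearly unequal, from .0167 to just under .03.

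The trial remains feasible and 495 is unaffected, so this should be corrected but does not threaten the design.

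**What to change.** - Name the three contrasts as the tests of the relapse count: guided vs app, app vs assessment-only, and guided vs assessment-only.
- Fix the multiplicity rule. Either test each at .05/3, or run pairwise tests at 0.05 only after a significant joint three-arm test. With three arms the second option keeps family-wise error at or below 5%.
- Analyse the count with a negative binomial or recurrent-event rate model, with log follow-up time as offset and robust standard errors, and report rate ratios.
- Replace the 80% omnibus statement with contrast-level power at 495, giving the assumed pattern of means.
- Correct 238 to 244 if that figure is kept; this does not change the 495 target.

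The cost is wording and routine software, with no added participants or data. The stated power for the two neighbouring contrasts will look less favourable: 56–65% each at .05/3, or 72–79% with the gated order, under even spacing. The offset adjusts for unequal observation time but does not cure dropout that depends on relapse.
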